Flow Rate In the United States, to meet 42 CFR Part 84 requirements, PAPR blowers must proc NIOSH approved minimum flow rate. Values: 170 liters/minute (Lpm) for loose-fit facepieces and 115 Lpm for tight-fitting facepieces		
Hood	A respiratory inlet covering that completely covers the head/neck and may cover portions of the shoulders and torso.	
Helmet	Differs from a hood only in that it provides a rigid head covering	
Loose-fitting facepiece (LFF)	A respiratory inlet covering that is designed to form a partial seal with the face. Value: loose-fitting inlet coverings are used on supplied air respirators (SAR) as well as PAPRs. In the U.S., the minimum airflow for LFFs is 170 L/min (CFR, 1995).	
Program Protection Factor (PPF)	An estimate of the respiratory protection provided to a worker in the context of a specific respirator program.	
Simulated Workplace Protection Factor (SWPF)	SWPF is deduced by measuring a test atmosphere concentration outside (Co) while also testing the inside (Ci) of a properly functioning respirator in a laboratory using test exercises designed to simulate work. Value: Calculated as 0 to continuous, and is expected to at minimum be equivalent to APF value designated for the device (at least 25 or 1000 for PAPRs)	

Workplace Protection Factor (WPF)	A measure of the protection provided in the workplace, under the conditions of that workplace, by a properly selected, fit tested and functioning respirator while it is correctly worn and used.
U.S. licensed health professional	An individual who is qualified by education, training, and licensure who performs a professional service within his/her scope of practice.

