Clayton et al. (2002) measured SWPF laboratory performance of two full facepiece PAPRs approved under European performance criteria (BSI, 1992). Limitations included failure to fit test the subjects, protrusion of spectacle temple bars through the face seal, and simulated battery failures, and lack of work rate or flow rate reported outcomes. The authors continuously measured facepiece penetration of a sulfur hexafluoride (SF $_6$) challenge over 3-4 hours of simulated asbestos removal. Work rate was not reported, but the tasks described would likely be classified as moderately heavy work. Neither airflow to the facepiece nor facepiece pressure was

monitored during the tests. Overall reported SWPF values ranged from 2,000 to 20,000 over 20 simulations. The remaining simulation had a SWPF of 400. Our current protocol also incorporates full-facepiece PAPRs to compare their performance to PAPRs with loose-fitting hoods/facepieces, and the design will remove the limitations experienced during this trial.

Seiple and Pappas (2003) tested the 3M Breathe Easy PAPR with a butyl rubber hood in a SWPF study. The challenge agent was 20-40 mg/m³ polydisperse corn oil with a mass median aerodynamic diameter (MMAD) of 0.4-0.6 µm. Laser photometry was used to measure challenge aerosol and penetration on the operating (blower on) PAPR. U.S. Army standard sampling probes were used to collect in-hood samples. Seven standard fit testing exercises plus "sight the rifle," "reach for the floor and ceiling," and "on hands and knees, look left and right" were performed for one minute each by 24 test subjects. All SWPFs were greater than 20,000. Our current protocol also employs a varied set of dynamic exercises to determine the effect of each exercise on particle penetration in the PAPR hood or facepiece, however additionally studies flow rate effects.

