Cohen et al. conducted a large SWPF study of loose fitting PAPRs with HEPA filters and supplied air respirators used in the pharmaceutical industry (Cohen et al., 2001). Five PAPRs with hoods, one loose-fitting facepiece PAPR, and six hood-style SARs were tested. Seventeen volunteers (60% men, 40% women) wore the devices in a test chamber. A polyethylene glycol 400 aerosol at a concentration of approximately 17 mg/m³ and a mass median diameter of 0.44 μm was used as the challenge atmosphere. Light-scattering photometry was used to measure C₀ and C_i aerosols; the C_i sample was taken with a nasal cannula beneath the subject's nose. The exercise regimen included 12 two-minute exercises that included "raising arm above head," "twisting at the waist while holding rod and raising and lowering arms," "scooping of pebbles," and "building of concrete block wall" in addition to standard fit testing exercises. Airflow from the PAPR blower or air supply and differential pressure inside the respirator were measured continuously during each test. Lower fifth percentile SWPFs for the five PAPRs ranged from 150,000 to >250,000, defined as the limit of quantification for the experimental setup. Supplied air devices had fifth percentile SWPFs ranging from 86,000 to >250,000, except for one SAR. The fifth percentiles for this device were < 20: the authors attributed this poor performance to an apparent design flaw: The device did not have a bib to tuck into the wearer's clothing. Fifth percentiles for the same device with a bib were four orders of magnitude higher. Additional insights can be gained from the airflow and differential pressure measurements Cohen et al. reported. Mean air flow rates in their study were all above the NIOSH required minimum of 170 L/min, ranging from 176 to 304 L/min. The poorly performing SAR had a mean flow rate of 234 L/min and a minimum of 203 L/min. One hood-style PAPR and the LFF PAPR, were found to have occasional airflow measurements as low as 132 and 149 L/min, respectively. Interestingly, the hood-style PAPR had slightly higher fifth percentile SWPFs. The authors noted "There was no consistent pattern among the relationship of pressure measurements taken inside the facepiece [sic] and the corresponding SWPFs recorded." The Cohen et al. study appears to support the ideas suggested later by several studies conducted by Johnson and Koh (Johnson et al., 2008; Koh et al, 2011; Johnson et al., 2011; Koh and Johnson, 2012). That is, design characteristics may affect the protective performance of loose-fitting devices in addition to their rate of airflow, and higher flow rates do not assure a higher level of performance. The effect of occasional negative pressure spikes on the protection provided by loose-fitting respirators is not great; this could be related to dead volume, e.g., hood vs. LFF. Our current protocol design includes a diverse selection of PAPR designs to determine if the overall type of design (e.g., helmet

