Table 5. Phase II PAPR Models

#	PAPR MODEL	OSHA APF	RIC DESIGN
			tight-fitting full
1	Bullard EVA	1000	facepiece
	2504.00	1000	tight-fitting full
2	MSA OptimAir	1000	facepiece
3	3M Versaflo		
	hood (S-403L (M/L size)	1000	loose-fitting full hood
	hood (S-403S (S/M size)	1000	
4	ILC Dover Sentinel XL		
	S-2019-10 (one-size)	1000	loose-fitting full hood
5	Bullard EVA		
	20TIC hood (one-size)	1000	loose-fitting full hood
6	Maxair Helmet CAPR w/ HE filter (Bio-Medical Devices, Inc.)		
	2261-01ML	25	loose-fitting full hood
	2261-01SM	25	
7	Maxair Helmet CAPR w/ HE filter (Bio-Medical Devices, Inc.)	25	loose-fitting facepiece

[figure not shown]

	3M VersaFlow w/ S133 cuff		
8	facepiece	25	loose-fitting facepiece

Flow Rates

 The two PAPR airflow rates tested in Phase II include: 1) 170 L/min for loose-fitting PAPRs and 115 L/min for tight-fitting PAPRs (based on the current NIOSH minimum certification airflow rates) and 2) 125 L/min for loose-fitting PAPRs and 100 L/min for tight-fitting PAPRs (experimental airflow rates below the NIOSH certification requirement). Flow rates at and below the NIOSH certification minimum, PAPRs will be modified and therefore not NIOSH certified. Modifications to these devices will reduce airflow by one of two ways as determined by the study team: 1) controlling voltage to the PAPR motor, 2) installing a 3-way valve into the blower hose (if equipped) to bleed-off excess flow (Figure 3).

Figure 3. Subject Wearing a PAPR with Fixed Airflow Valve

Simulated Workplace Protection Factor

SWPF testing will take place in both Phase II and Phase III, following the work rate determination in Phase I. Test subjects wearing PAPR will enter the test chamber and complete the exercise regimen (Table 3.) against a corn oil challenge aerosol.

For this test, a TSI Rear Light Scattering Laser Photometer, model 8587A, will be used to measure aerosol concentration inside of the respirators. A TSI model 8520, Dustrak Aerosol Monitor will be used to monitor chamber particle concentrations. Data collected by the laser photometer will be recorded on the NIOSH Dynamic Fit Software. Data will be analyzed using a three-way repeated measures ANOVA with subject number, model, and work rate, and the log transformed SWPF of each test as the dependent variable. The relative importance of each variable to PAPR performance will be determined. The SWPF will be calculated in two steps as follows:

1. Ratio of the Upstream and Downstream Particle Concentrations

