
$$SWPF_{i} = \frac{C_{out}}{C_{in}}$$

 Where: SWPF = simulated workplace protection factor; i = exercise number; $C_{out} = exercise$ upstream particle concentration; $C_{in} = exercise$ downstream particle concentration

2. Overall SWPF for Each PAPR Model

$$Overall SWPF = \frac{n}{\frac{1}{SWPF_1} + \frac{1}{SWPF_2} + \cdots + \frac{1}{SWPF_{n-1}} + \frac{1}{SWPF_n}}$$

Where: $SWPF_n = simulated$ workplace protection factor for a given exercise; n = number of exercises used during an SWPF test.

Test Chamber

The SWPF testing will be conducted inside a 16' x 16' x 10' charged corn oil test chamber in Building 40 of the National Personal Protective Technology Laboratory in Pittsburgh, PA. SWPF test setups are displayed in Figures 4A and 4B.

A 99% stock corn oil (CAS #8001-30-7) with the commercial product names Maise/Maize, Maydol, and/or Mazola oil will be used for test aerosol. It will be aerosolized using an MSP Model 2045 High Output Aerosol Generator capable of maintaining 5 to 100 mg/m³ of corn oil challenge aerosol concentrations for the required test duration. For SWPF testing, the test chamber will be maintained at ~20-40 mg/m³. The output aerosol will be dried with 30% dilution air, followed by neutralization with a Kr-85 charging source before entering into the exposure testing chamber. The aerosol will have a Mass Median Aerodynamic Diameter (MMAD) of 0.4 to 0.6 μ m, with a geometric standard deviation of less than 2.0. This size distribution will be measured once daily using a Scanning Mobility Particle Sizer (SMPS) system. This system is comprised of the TSI model 3080 Electrostatic Classifier, TSI model 3775 Condensation Particle Counter, and 3081 Long Differential Mobility Analyzer (DMA).

The aerosol in the exposure chamber will be mixed using four internal fans positioned in the top four corners of the charged corn oil test chamber, and the chamber conditions will be tracked by a humidity/temperature sensor. Corn oil aerosol particles will be continuously dispersed into the chamber, while an open exhaust port will remove excess air and maintain neutral pressure.

Figure. 4A: Aerosol Chamber Testing System for Loose-Fitting PAPRs

[figure not shown]
[figure not shown]

Figure. 4B: Aerosol Chamber Testing System for Tight-Fitting PAPRs

Subject Monitoring

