8.2 Phase II Statistical Methods

For Phase II SWPF values will be calculated as the ratio of time-weighted average C_{out}/C_{in} for the summation particles across the size range measured, for each exercise. Overall SWPF for each attempt of a subject wearing each respirator model will be determined by taking the harmonic mean of the SWPF for all individual SWPF exercises. The performance of the respirators across the size range measured will be determined using the 5th percentile and geometric mean (GM) SWPF values. The 5th percentile SWPF value will be calculated from the formula GM/GSD^{1.645}, where GSD is geometric standard deviation. A log transformation of the data will be done to adjust for a skewed distribution and extreme outliers as described previously (OSHA 2006). For Phase II, a normality test will be conducted for the log transformed dependent variable (i.e. SWPF value for each test) first. If the normality holds, a three-way repeated measures ANOVA will be performed with subject number, respirator model, and work rate/exercise regime and flow rate of the respirator as independent variables, otherwise a Generalized Estimating Equation (GEE) model will be fit using the same set of independent variables. A full factorial design, which includes the main effects of work rate and flow rate, and their interaction, will be used. In this study phase, the data will be analyzed after all 25 subjects complete the first of three replicates with each PAPR and all three flow rates to estimate statistical effects and conduct a power analysis.

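### Section 8.2 makes no provision for SWPF values at the photometer's quantification limit; if that limit binds, the GM/ANOVA flow contrast is biased towards protection being maintained

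*Protocol*

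**What the plan says.** Section 8.2 sets out the chain for Phase II. Each exercise gives an SWPF as the ratio of outside to inside concentration. The overall value per test is "determined by taking the harmonic mean of the SWPF for all individual SWPF exercises". Values are log-transformed, and performance is described by the geometric mean and a 5th percentile: "The 5th percentile SWPF value will be calculated from the formula GM/GSD^{1.645}, where GSD is geometric standard deviation". On the model it says: "If the normality holds, a three-way repeated measures ANOVA will be performed with subject number, respirator model, and work rate/exercise regime", with flow rate also listed and a GEE on the same variables if normality fails. Section 8.3 carries the approach into Phase III without the flow effect.

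Table 1 gives the range of SWPF as follows: "Calculated as 0 to continuous, and is expected to at minimum be equivalent to APF value designated for the device". Section 3.3 names the in-mask instrument, "For this test, a TSI Rear Light Scattering Laser Photometer, model 8587A, will be used to measure aerosol concentration inside of the respirators", without a quantification limit. It also sets the challenge level: "For SWPF testing, the test chamber will be maintained at ~20-40 mg/m³".

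Two studies in section 1.2 bear on the point. In a light-scattering photometer study at about 17 mg/m³: "Lower fifth percentile SWPFs for the five PAPRs ranged from 150,000 to >250,000, defined as the limit of quantification for the experimental setup". In a corn-oil laser-photometry study of a hood PAPR at 20-40 mg/m³: "All SWPFs were greater than 20,000". Section 3.1, on the other hand, speaks of SWPF means in the thousands, with a GSD of about 1.5 to 3.5.

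**The concern.** SWPF is outside concentration divided by inside concentration. Once the inside reading falls to the photometer's limit, the test shows only that SWPF is at least the outside concentration divided by that limit. Such a value is right-censored. A geometric mean, a GSD or an ANOVA that takes the ceiling as the value is wrong by an amount that depends on the share of tests at the ceiling. That share is larger in the better-protected condition, here the NIOSH-minimum flow.

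Primary objective (a) is the relation between flow rate and SWPF, and section 2.0 asks whether protection is maintained at lower flow. Clipping at a common ceiling can only reduce a difference in mean log SWPF, so the error in that contrast runs towards no loss. The GEE fallback does not help: a pile-up at the ceiling may fail the normality test and trigger the switch, but GEE still models those values as measured.

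**Working it through.** **Plan's own figure.** There is none on this point. The protocol gives no quantification limit for this set-up. Its only precision statement (25 subjects, effect size 0.4) does not involve one.

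**Inputs from the protocol.** GSD 1.5 to 3.5 (section 3.1); chamber 20 to 40 mg/m³ (section 3.3); a cited limit of 250,000 at about 17 mg/m³, and a lowest cited 5th percentile of 150,000 (section 1.2).

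**Assumptions.** Lognormal SWPF; readings beyond the ceiling recorded as the ceiling; a true halving at reduced flow; minimum-flow 5th percentile 150,000; the cited limit is a fixed in-mask concentration, 17/250,000 = 6.8 × 10⁻⁵ mg/m³. The ceiling L is then 250,000 × 20/17 ≈ 294,000 or 250,000 × 40/17 ≈ 588,000. That study used another aerosol and sampling set-up, so these ceilings are illustrative.

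**Formulas.** Let X = ln SWPF with mean μ and SD σ = ln GSD, c = ln L, z = (c − μ)/σ and Y = min(X, c).
- Share above the ceiling = 1 − Φ(z)
- E[Y] = μΦ(z) − σφ(z) + c(1 − Φ(z))
- E[Y²] = (μ² + σ²)Φ(z) − σφ(z)(μ + c) + c²(1 − Φ(z))
- Apparent GM = exp(E[Y]); apparent GSD = exp(SD[Y])

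At minimum flow μ = ln 150,000 + 1.645σ; at reduced flow μ is lower by ln 2.

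**One case in full** (GSD 2.5, L = 294,000). σ = 0.916, μ = 11.918 + 1.507 = 13.426, c = 12.592, z = −0.910. The share above is 82% and the apparent GM 268,700 (true 677,000). At reduced flow z = −0.154, the share above is 56% and the apparent GM 218,000. The apparent ratio is 218,000/268,700 = 0.81 against a true 0.50.

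**All cases** (true ratio 0.50; true 5th percentiles 150,000 and 75,000):

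| Ceiling | GSD | Above ceiling, minimum flow | GM ratio | GM/GSD^1.645, minimum / reduced | Its ratio |
|---|---|---|---|---|---|
| 294,000 | 1.5 | 49% | 0.58 | 168,000 / 76,000 | 0.45 |
| 294,000 | 2.5 | 82% | 0.81 | 175,000 / 98,000 | 0.56 |
| 294,000 | 3.5 | 87% | 0.87 | 167,000 / 104,000 | 0.62 |
| 588,000 | 1.5 | 4% | 0.50 | 153,000 / 75,000 | 0.49 |
| 588,000 | 2.5 | 56% | 0.67 | 196,000 / 91,000 | 0.46 |
| 588,000 | 3.5 | 71% | 0.76 | 208,000 / 107,000 | 0.52 |

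The GM ratio is never pushed below 0.50. The ratio of GM/GSD^1.645 falls below 0.50 in three of the six cells, because clipping compresses the GSD more at minimum flow and so raises that percentile more. The reduced-flow percentile is overstated by up to 107,000/75,000 = 1.43.

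**Chamber level.** At GSD 2.5 the apparent minimum-flow GM is 436,000 with the 588,000 ceiling and 268,700 with the 294,000 ceiling. Moving from 40 to 20 mg/m³ alone therefore multiplies it by 0.62.

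**With the harmonic mean included.** A simulation used 2,000 runs, 25 paired subjects, ten exercises each clipped at L, then harmonic mean, log and paired t-test, with half of the log variance between subjects, GSD 2.5 and a true ratio of 0.50:

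| GM/L | Exercises above ceiling, minimum / reduced | GM ratio | Power |
|---|---|---|---|
| 0.02 | 0% / 0% | 0.50 | 1.00 |
| 1 | 50% / 22% | 0.62 | 0.99 |
| 3 | 88% / 67% | 0.85 | 0.86 |
| 10 | 99% / 96% | 0.99 | 0.04 |

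**If SWPFs are in the thousands.** At GM 5,000 or 9,000 with the 294,000 ceiling, at most 0.3% of tests are above it and the GM ratio stays at 0.50. At GM 50,000 at most 8% are above it and the ratio is 0.50 to 0.52.

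**Against the APF.** A true 5th percentile of 1,000 at GSD 3.5 means a GM of 1,000 × 3.5^1.645 ≈ 7,850, which is 0.03 of a 250,000 ceiling. The formula then returns about 1,004. With a ceiling of only 20,000 it would return about 1,250.

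**The case against.** The strongest reply is that the protocol never says readings at the limit will be scored as measured. That is inferred from silence, and a rule could stand in a statistical analysis plan or laboratory procedure that is not shown. This is fair as far as it goes, and the range in Table 1 describes the type of variable rather than denying a ceiling. But section 8.2 does fix the percentile formula and the models. A later rule for censored values would have to replace them, not just add to them.

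Second, no limit for this photometer is given. The 250,000 comes from a study with another aerosol, nasal-cannula sampling and mean flows of 176 to 304 L/min, whereas this study runs loose-fitting devices at 170 and 125 L/min and tight-fitting ones at 115 and 100. The table above needs true minimum-flow GMs of 292,000 to 1,178,000, while section 3.1 speaks of thousands. This stands: whether the limit binds is open. The protocol's own sources place devices on both sides, and four of the eight models are hoods.

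Third, the harmonic mean is dominated by the lowest, least-censored exercises. The simulation includes that step and still shows attenuation, though power is barely touched until most exercises are at the ceiling.

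A reader might infer that the quoted formula itself always shrinks a loss at reduced flow, or that the plan would pass an unsafe device. Neither is supported. The contrast in GM/GSD^1.645 is exaggerated in half of the cells, and against an APF of 25 or 1,000 a percentile of 107,000 instead of 75,000 changes nothing.

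**Conclusion.** The point holds conditionally and is worth acting on. Section 8.2 commits to estimators that need fully observed values, in a field where the protocol itself cites PAPR results beyond the quantification limit.

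- **If the limit binds,** the GM/ANOVA flow contrast is biased towards maintained protection. A true 0.50 appears as 0.58 to 0.87 at a 294,000 ceiling and as 0.50 to 0.76 at 588,000.
- **The level of GM/GSD^1.645** is biased, upwards in all six cells shown. Its flow contrast moves in a direction that depends on the share censored.
- **If SWPFs are in the thousands,** there is no material effect.
- **Conclusions against an APF of 25 or 1,000** are little affected in either case. What is at stake is the size of the flow effect, not passing the APF.

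The figures rest on lognormality, recording at the ceiling, the rescaled limit from another set-up, and the assumed halving.

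**What to change.** In section 3.3, state the photometer's quantification limit from calibration. In section 8.2, define each test's ceiling as its outside concentration divided by that limit, flag exercise and overall values above it, and report the share flagged by model and flow rate. Where only some of the ten exercises are flagged, the overall harmonic mean is known only as a range (flagged exercises set to the ceiling, or contributing zero to the sum of reciprocals) and should be entered as such.

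Where any value is censored, estimate the flow contrast from a censored lognormal mixed model with subject as a random effect. Replace GM/GSD^1.645 by the empirical 5th percentile when it lies below the ceiling, or by a censored maximum-likelihood estimate. Where nothing is censored, keep the planned analysis.

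The cost is protocol or SAP wording and a little more analysis work, with no extra tests. Intervals will be wider for heavily censored devices. The empirical percentile will be imprecise, since each model and flow rate has 25 × 2 = 50 overall values.

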APPENDIX M. PHASE II QUESTIONNAIRE: ASSESSING PAPR FLOW RATE EFFECT	
APPENDIX N. PHASE III QUESTIONNAIRE: ASSESSING USER WORK RATE EFFECT	74
APPENDIX O. NPPTL DAILY POST-TEST EVALUATION	75
APPENDIX P. EMERGENCY DECISION MAKING PROTOCOL	77
APPENDIX Q. STUDY INVESTIGATORS	78
APPENDIX R. DELEGATION OF AUTHORITY LOG	811
APPENDIX S. IRS FORM W-9	83
APPENDIX T. TEST SUBJECT PAYMENT FORM	889
APPENDIX U. NPPTL GENERAL PHOTO RELEASE	900

PROTOCOL SUMMARY

This is a controlled study to examine methods for quantifying powered air-purifying respirator (PAPR) performance, usability, and flow rates, as well as to improve effectiveness in healthcare while maintaining device safety and efficacy. Tests will be conducted at the Centers for Disease Control and Prevention (CDC) campuses in Pittsburgh, PA with a sample size of 25 evaluable subjects, and up to 75 subjects enrolled. Subjects will be considered evaluable if they meet screening requirements and fall within an available NIOSH/NPPTL Bivariate Panel cell category to provide representation of facial sizing for the U.S. workforce (Zhuang et al., 2007), and complete all study interventions within at least one of three phases. **Phase I** of this study will collect baseline physiological data to determine typical work rates for ten exercises identified in healthcare, without wearing a PAPR. Subjects will complete **Phase II**, replicating the ten activities from Phase I, while trialing eight models of PAPRs at two flow rates (NIOSH minimum and a reduced rate below NIOSH minimum flow rate), to determine simulated workplace protection factor (SWPF) values. Phase III will include two exercise regimens comprised of three exercises each, and subjects will trial eight models of PAPRs with the flow rate held constant at NIOSH approved minimum standard rate, to determine work rate effect on SWPF values when exercise regimen is modified by task order, work rate, and time.

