3.1 Screening Design

A sample of 25 evaluable test subjects will be included in this study and up to 75 subjects enrolled. Following recruitment and consent, subjects will undergo facial measurements to determine if they fit into an available cell category of the NIOSH/NPPTL Bivariate Panel (Fig. 2 and Table 2) used to collect facial dimension representation of the US workforce. The sample size of 25 subjects was first proposed by Landsittel et al. (2014) and later supported by interpanel variability results reported by Zhuang et al. (2015) and Liu et al. (2016). The numbers in each cell in Figure 2 represent cell category number. The numbers in parentheses indicate the number of subjects to be sampled in that category. When the subject's face length or face width fall on the boundaries, the subject is classified into the higher number cell category.

A sample size of 25 subjects (calculated using G*Power 3.1.9.2.) also provides the researchers with acceptable levels of precision to estimate population parameters and to compare SWPF results across flow rates and work rates. Previous research by the PI has found the standard deviation among sets of SWPF scores for PAPRs to be considerably low when compared to the average. Studies have shown a geometric standard deviation of ~1.5-3.5—while SWPF mean values can be in the thousands. This mean to standard deviation ratio allows for very precise estimates of population parameters with relatively small samples of 25 subjects. It also makes comparison among conditions of the study to be precise. However given that small differences in

SWPF can make a meaningful practical difference the researchers' goal is to estimate precise population parameters and detect small differences between conditions as significant. A sample of 25 and a repeated measures design (as explained below) allow the researchers to detect an effect size of 0.4 as significant. This effect size means that a little less than one half of the standard deviation can be detected as significant when dependent means are compared.

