3.3 Phase II

the GXT.

Phase II is designed to test flow rate effects on individual exercises & regimen overall SWPF values. This phase will include the 25 evaluable subjects from Phase I if they are interested in continued participation. If subjects from Phase I decline or are no longer eligible, additional subjects may be consented and screened for recruitment utilizing the modified screening requirements from Phase I (Appendix A, Study Calendar 1). Phase II will use the exercise regimen (Table 3.) and work rates determined in Phase I, with eight different PAPR models and two flow rates for each PAPR. Subject's will complete one 30-minute regimen = ten, 3 minute exercises completed in sequential order from light to hard work rates with breaks following the hard exercises (see Section 3.2) for sequence. 25 subjects x 8 PAPR models x 2 flow rates x 2 regimen replicates = 800 overall SWPF values (based on 10 exercises). Three Way Repeated Measures ANOVA will be used to analyze the data.

Each subject will come in to test 2 PAPRs and 2 flow rates per visit for approximately 3 hours, 392 for a total of 4 visits (~12 total hours) to complete the first replicate of tests. The subjects will 393 repeat the same procedure for the second replicate, meaning each subject will complete Phase II 394 over the course of 8 visits of approximately 3 hours per visit (~24 total hours). It is estimated that this phase will take 6 to 9 months (November 2019-July 2020). 396

PAPR Models

391

395

397

398

399

400

401

402

403

404

405 406

407

408 409

410

Eight PAPR models (4 PAPRs with loose-fitting hoods, 2 loose-fitting facepiece PAPRs with helmets, and 2 tight-fitting PAPRs) were selected for this study (Table 5.). The models were selected based on: 1) prevalence of respirators in healthcare (Wizner, 2016) and 2) their commercial availability. The assigned protection factors for each PAPR is 25 or 1000. Tight fitting full facepieces (models 1-2) have a tight seal along the chin and sides of face. Loosefitting full hoods (models 3-6) have a shroud covering the shoulders down to the mid-torso. Loose-fitting facepieces (models 7-8) have a cuff that loosely contacts the chin and the sides of the face. Each PAPR device weight will be measured and recorded. All PAPR devices used in this study will be set at the same airflow rate. Each subject will be asked to complete the comfort survey after each PAPR tested with all three flow rates in Phase II (Appendix M).

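### The choice between repeated measures ANOVA and GEE rests on a normality test of the pooled log SWPF values, when the assumption concerns the model residuals

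*Protocol*

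**What the plan says.** Section 8.2 sets a two-step rule for the Phase II analysis. Step one: "a normality test will be conducted for the log transformed dependent variable (i.e. SWPF value for each test) first". Step two depends on the outcome. "If the normality holds, a three-way repeated measures ANOVA will be performed with subject number, respirator model, and work rate/exercise regime and flow rate" entered as independent variables; "otherwise a Generalized Estimating Equation (GEE) model will be fit using the same set of independent variables". The section adds: "A full factorial design, which includes the main effects of work rate and flow rate, and their interaction, will be used". Section 8.3 applies the same approach to Phase III without the flow factor.

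The size of the data set is given in Section 3.3: "25 subjects x 8 PAPR models x 2 flow rates x 2 regimen replicates = 800 overall SWPF values". Table 5 lists eight devices, five with an APF of 1000 (models 1 to 5) and three with an APF of 25 (models 6 to 8).

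Residuals are not mentioned anywhere in the statistical sections. The protocol names no particular normality test and no level for it. For the GEE it names no variance estimator, test statistic or reference distribution.

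**The concern.** A repeated measures ANOVA assumes that the errors are normal once the model terms have been taken out. It does not assume that the outcome is normal when all cells are thrown together. Pooled log SWPF is a mixture over eight devices and two flow rates, and each subject contributes 8 x 2 x 2 = 32 values. Two features can make a pooled test reject although the ANOVA assumption is met:

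- Different device means make the pooled distribution skewed or bimodal.
- Only 25 subject effects sit behind 800 values, so the values are far from independent.

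The gate therefore answers a question unrelated to the assumption it is meant to protect. A large effect of respirator inlet covering design, which the study lists as a secondary objective in Section 2.2, is itself enough to switch the analysis. The switch leads to a method whose usual large-sample tests are less reliable with 25 clusters than the ANOVA they replace.

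**Working it through.** The plan states no error rate for this rule, so there is no figure of its own to reproduce beyond the count: 25 x 8 x 2 x 2 = 800.

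**Inputs from the protocol.** 25 subjects, 8 models, 2 flow rates, 2 replicates (Section 3.3). GSD 1.5 to 3.5 (Section 3.1). Models 1 to 5 against models 6 to 8 as the two device groups (Table 5).

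**Assumptions.** Shapiro-Wilk as the normality test. 5% level for it and for the effect tests. Exactly normal errors on the log scale. A subject effect that carries 30% of the within-device variance, with 20% and 50% as alternatives.

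**Step 1: how often the gate rejects sound data.** With models 6 to 8 lower than models 1 to 5 by the stated factor, 300 runs per cell and a 30% subject share, the pooled test on 800 values rejects in:

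| Device gap | GSD 1.5 | GSD 2 | GSD 2.5 | GSD 3.5 |
|---|---|---|---|---|
| none | 15% | 10% | 9% | 10% |
| 2-fold | 66% | 12% | 8% | 9% |
| 4-fold | 100% | 93% | 41% | 10% |
| 10-fold | 100% | 100% | 100% | 83% |
| 40-fold | 100% | 100% | 100% | 100% |

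The same test on the residuals of the same data rejects in about 3% to 8% in every cell, around the nominal 5%. Varying the subject share moves the rate to about 6% to 37% when devices are equal or 1.67-fold apart, and to about 10% to 47% at a 4-fold gap with GSD 2.5 to 3.5. Monte Carlo error at 300 runs is about 2 percentage points near 83%: sqrt(0.83 x 0.17 / 300) = 0.022.

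**Step 2: what the fallback does, if it is the usual uncorrected form.** For a balanced design with K = 25 subjects, the robust Wald statistic is W = K/(K - 1) x Hotelling T2, and T2 = (K - 1)q/(K - q) x F(q, K - q). Hence

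P(W > c) = P( F(q, 25 - q) > c x (25 - q)/(25q) ), where c is the 95% point of chi-square on q df.

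| Effect | q | c | F threshold | Type I error |
|---|---|---|---|---|
| Flow | 1 | 3.841 | 3.841 x 24/25 = 3.688 | 6.7% |
| Work rate or work rate x flow, three work rates | 2 | 5.991 | 5.991 x 23/50 = 2.756 | 8.5% |
| Model or model x flow | 7 | 14.067 | 14.067 x 18/175 = 1.447 | 24.8% |
| Exercise, ten levels | 9 | 16.919 | 16.919 x 16/225 = 1.203 | 35.7% |

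Simulation of the 7-df model x flow test gives 24.1%, and fitted exchangeable GEEs with robust covariance give 24% to 26%. Scaling the sandwich by K/(K - 1) lowers the 7-df figure only to 22.7%.

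**Step 3: the branch that is abandoned.** In the same simulations, where sphericity holds, the ANOVA has a type I error of 4.8% for flow and 4.6% for model x flow.

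**The case against.** Four points can be made for the plan.

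*The GEE is not specified as uncorrected.* A reader might infer that the protocol commits to tests with 25% type I error. It does not. The variance estimator and reference distribution are details that a protocol commonly leaves to an SAP, and a small-sample correction there would remove most of the excess. This stands: the figures in step 2 are conditional. Nor is 25% a ceiling, since tests with more df do worse.

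*The primary questions are little affected.* Section 2.1 names flow rate and work rate as primary; device design is secondary. Even with an uncorrected GEE, flow runs at 6.7% and a three-level work rate at 8.5%. This also stands.

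*Misrouting is not certain.* A reader might take the 40-fold ratio of APFs as the expected gap in SWPF. Table 1 treats the APF as a minimum that the SWPF should reach, not as a mean. In the large pharmaceutical-industry study reviewed in Section 1.2, the PAPRs' lower fifth percentiles run from 150,000 to above 250,000, a ratio of 250/150 = 1.67 apart from censoring at the upper limit. At such gaps the gate often passes. This stands as a limit on frequency. It does not make the pooled outcome the right quantity to test.

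*Missing tests.* A reader might infer that the ANOVA branch drops every subject who lacks one of the 32 tests. The documents do not support this. Replicate is not among the listed factors, so averaged replicates need only 8 x 2 = 16 filled cells, and no missingness rate is given. The restriction to completers comes from the evaluability definition in the Protocol Summary ("complete all study interventions within at least one of three phases") and applies whichever model is chosen.

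**Conclusion.** The rule in Section 8.2 is wrong as written: it tests the pooled outcome where the assumption concerns residuals, and it lets that test choose the model. How often this misroutes valid data depends on the device gap relative to the GSD. Misrouting ranges from little more than nominal when devices are alike and subject correlation is low, to near certain at a 4-fold gap with GSD 2 or less and at a 40-fold gap throughout the stated GSD range. These rates rest on Shapiro-Wilk at 5% and normal errors, both assumed.

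The harm after misrouting is conditional on an uncorrected robust Wald chi-square test. It is then small for the flow effect, modest for work rate, and serious for 7-df comparisons of models or of model by flow. The point should be corrected before analysis. It does not threaten the primary flow comparison in any large way.

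**What to change.** Remove the normality gate on the outcome in Section 8.2, and thereby in Section 8.3. Prespecify one model for log SWPF: either the repeated measures ANOVA already named, or a linear mixed model with small-sample degrees of freedom. Check normality on that model's residuals. Moving the check to residuals is the minimum change and is enough to cure the gate.

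If a GEE is kept as a fallback, state that it uses a small-sample corrected variance with a t or F reference distribution.

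The cost is a few sentences of wording and minor programming in standard software. No visits, subjects or measurements change.
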